4.3 Justification for Dose

Dosing for pediatric and adult subjects will be based on current FDA-approved regimens for XLH and TIO. Doses will be adjusted to target a serum phosphate level between -1 and +2 standard deviations for age and sex. The justification for targeting a mid-high normal phosphate level is based on the following rationale: FD bone is inherently structurally unsound and poorly mineralized, and patients with FD have an overall high prevalence of skeletal morbidity compared to other FGF23 excess disorders. Even mild degrees of hypophosphatemia have been associated with increased fractures and deformities in patients with FD [1-4]. It is therefore feasible that patients with FD may experience clinical benefit from maintaining a higher therapeutic target for serum phosphate levels. The current study provides an important opportunity to investigate the safety and efficacy of this approach in patients with FD and is supported by the well-established and favorable safety profile of burosumab in phase 2 and 3 studies.

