5 STUDY POPULATION

5.1 Inclusion Criteria

In order to be eligible to participate in this study, an individual must meet all of the following criteria:

1. Confirmed diagnosis of fibrous dysplasia
2. Serum phosphate <10th percentile for age and sex, AND intact serum FGF23 ≥ 30 pg/mL[16]
3. Age ≥ 1 year
4. Provision of signed and dated informed consent/assent form

5. Stated willingness of subject or Legally Authorized Representative (LAR) to comply with all study procedures and availability for the duration of the study
6. For females of reproductive potential: agreement to use highly effective contraception for during study participation. Highly effective contraception methods include:
 - Total abstinence (when this is in line with the preferred and usual lifestyle of the participant). Periodic abstinence (e.g., calendar, ovulation, symptothermal, post-ovulation methods) and withdrawal are not acceptable methods of contraception
 - Female sterilization (have had surgical bilateral oophorectomy with or without hysterectomy) or tubal ligation at least six weeks before taking study treatment.
 - Male sterilization (at least 6 months prior to screening). For female participants on the study the vasectomized male partner should be the sole partner for that participant.
 - Combination of the following (a+b or a+c, or b+c):
 - a. Use of oral, injected or implanted hormonal methods of contraception or other forms of hormonal contraception that have comparable efficacy (failure rate <1%), for example hormone vaginal ring or transdermal hormone contraception
 - b. Placement of an intrauterine device (IUD) or intrauterine system (IUS)
 - c. Barrier methods of contraception: Condom or Occlusive cap (diaphragm or cervical/vault caps) with spermicidal foam/gel/film/cream/vaginal suppository
7. For males of reproductive potential: use of condoms or other methods described above to ensure effective contraception with partner
8. Minimum body weight of 7.5 kilograms

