5.3 Inclusion of Vulnerable Participants

5.3.1 Children

Children \geq 1 year will be included in this study. Burosomab has been well-studied in children with good safety and tolerability in phase 2 and 3 studies. Children with FD have higher incidence of hypophosphatemia compared to adults [17], and are at increased risk for growth-related and skeletal complications.

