6.1.2 Dosing and Administration

Burosomab initiation for pediatric and adult subjects will be based on currently approved regimens for XLH and TIO.

For pediatric subjects (age < 18 years) who weigh less than 10 kg, the starting dose is 1 mg/kg of body weight, rounded to the nearest 1 mg, administered every 2 weeks. For pediatric subjects who weigh 10 kg and greater, the starting dose regimen is 0.8 mg/kg of body weight, rounded to the nearest 10 mg, administered every 2 weeks. The minimum starting dose is 10 mg up to a maximum dose of 90 mg. For adults (age 18 years and older) the starting dose regimen is 0.5 mg/kg body weight, rounded to the nearest 10 mg up to a maximum dose of 90 mg, administered every 4 weeks.

After burosomab administration, doses will be titrated in an effort to achieve a target fasting peak serum phosphate level between -1 and +2 standard deviations for age and sex (**Table 5**). If the subject's peak serum phosphate level at week 2 remains below the target range, the subject's dose may be increased at week 4 by 0.2 to 0.5 mg/kg at the discretion of the Investigator. Doses will then continue to be titrated in increments of 0.2 to 0.5 mg/kg at 4-week intervals in individual subjects to achieve the target peak serum phosphate range. If the target range is not reached for patients >18 year and older, dosing may be administered at every 2-week dosing

intervals at the discretion of the PI and adjusted in increments of 0.2 to 0.5 mg/kg to a maximum dose of 90 mg every 2 weeks.

Table 5. Burosumab Target Phosphate Ranges for Pediatric and Adult Subjects

Age (years)	Normal Phosphate Range (mg/dL)	Target Peak Serum Phosphate Range (Z-score -1 to +2; mg/dL)
1 to <5	4.3 - 6.8	4.9 - 6.8
5 to <13	4.1 - 5.9	4.6 - 5.9
13 to <16 (girls)	3.2 - 5.5	3.8 - 5.5
13 to <16 (boys)	3.5 - 6.2	4.2 - 6.2
16-18	2.9 - 5	3.4 - 5
>18	2.5 - 4.5	3 - 4.5

From: summary of age and sex-partitioned reference intervals from the CALIPER study, including thousands of healthy children and adolescents from a multiethnic population and measured using the Abbot Architect analyzer [18].

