9 STATISTICAL CONSIDERATIONS

9.1 Statistical Hypothesis

This single-arm open-label trial is to gather preliminary information on the effectiveness and safety of burosumab in FD patients. Estimates for the primary and secondary endpoints will be provided.

- Primary Endpoint: The proportion of subjects achieving serum phosphate levels within the target range (Z-score -1 to +2) at Week 48.
- Secondary Endpoints:
 - Proportion of subjects achieving serum phosphate levels within the target range (Z-score -1 to +2) at Week 24
 - Adverse events and clinical safety laboratory tests for up to 4 weeks following the final burosumab dose (48 weeks for adults, 50 weeks for children).
 - Proportion of subjects achieving mean serum phosphate levels above the target range (Z-score >+2), as averaged across dose cycles between Baseline and Week 48
 - Change and percent change from baseline to post-baseline visits in serum phosphate, serum 1,25(OH)2D, ratio of renal tubular maximum reabsorption rate of phosphate to glomerular filtration rate (TmP/GFR)
 - Change in FD lesion activity using ¹⁸F-NaF PET/CT total lesion activity from baseline to 48 weeks

- Change and percent change in serum bone turnover markers, including procollagen 1 N-terminal propeptide (P1NP), beta crosslaps C-telopeptides (CTX), osteocalcin, and bone-specific alkaline phosphatase from baseline to 48 weeks
- Change in FD lesion histology and cell proliferation as assessed by minimally invasive bone biopsies from baseline to 48 weeks (adults with capacity to consent only) from baseline to 48 weeks
- Change from baseline to 48 weeks in muscle strength, range-of-motion, and walking speed (9-minute walk)
- Change from baseline to 48 weeks in patient reported outcomes measures: SF36 (adults), SF10 (children), Brief Pain Inventory (adults and children), Brief Fatigue Inventory (adults and children)

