9.4.2 Analysis of the Primary Endpoints

The 95% Clopper-Pearson exact confidence interval will be calculated for the proportion of subjects achieving serum phosphate levels within the target range (Z-score -1 to +2) at Week 48. The primary endpoint will be evaluated in the Efficacy Analysis Dataset.

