Assent Procedures for Minors: Where deemed appropriate by the clinician and the child's parent(s) or guardian, the child will also be included in all discussions about the trial and age-appropriate language will be used to describe the procedures and tests involved in this study, along with the risks, discomforts and benefits of participation. Assent procedures for minors may take place in person or remotely (e.g., via telephone or other NIH approved remote platforms used in compliance with policy, including HRPP Policy 303). Children under the age 7 will not be required to provide assent as they typically do not have the ability to fully understand the nature of research. Verbal assent will be obtained from minor participants age 7-12 who are old enough to understand the nature of the study and its implications but are too young to provide a signature. Written assent will be obtained from minors age 13 years and older whenever possible using a similar procedure as outlined in the above Standard Consent Procedures section. Dissent will be respected in children of all ages. The consent/assent process will be documented in the child's medical record, including the assessment of the child's ability to provide assent (verbal versus written) as applicable. If any enrolled subjects reach the age of 18 while enrolled in the trial, they will be contacted to determine whether they wish to continue on the trial and informed consent will be obtained from them at that time.

Privacy measures as described in the section titled Confidentiality and Privacy will be implemented for all minor in-person and remote consent process. During the remote consent process, minors with their parents/legal guardians and designated study investigators will view individual copies of the approved consent document at their respective locations. The assent process will be documented in the medical record.

Consent Procedures from Parents/Legal Guardians for Minors: Parental permission will be obtained in line with NIH policies regarding child custody.

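### Does the lack of a written age rule for reading Table 5 leave the Week 48 primary result open to choice?

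*Combined protocol and SAP*

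**What the plan says.** The primary analysis in Section 9.4.2 is a single estimate: "The 95% Clopper-Pearson exact confidence interval will be calculated for the proportion of subjects achieving serum phosphate levels within the target range". The timepoint is Week 48, the range runs from a Z-score of -1 up to +2, and the population is the Efficacy Analysis Dataset. Section 4.3 sets the target "between -1 and +2 standard deviations for age and sex". Table 5 in Section 6.1.2 turns it into mg/dL by age band, with separate rows for girls and boys from 13 to under 16, under the column heading "Target Peak Serum Phosphate Range (Z-score -1 to +2; mg/dL"). Footnote 1 of Table 6 sends the reader to Table 5 for the Z-scores that govern titration.

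The last two rows of Table 5 are labelled 16-18 (target 3.4 to 5) and >18 (target 3 to 4.5). The dosing text in the same section places the adult boundary at the 18th birthday: "For adults (age 18 years and older) the starting dose regimen" is given separately from the pediatric one. Section 10.1.1 provides for a change of age group, "If any enrolled subjects reach the age of 18 while enrolled in the trial", but only for consent.

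Section 9.1 also lists a secondary endpoint, "Proportion of subjects achieving mean serum phosphate levels above the target range" (Z-score above +2), averaged over dose cycles from Baseline to Week 48. No section states in words the age at which a phosphate value is scored.

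**The concern.** The bands differ enough for the choice to matter. A boy at 5.5 mg/dL is in range at 15 (4.2 to 6.2) and above range at 16 (3.4 to 5.0). A girl at 4.3 is below range at 12 (4.6 to 5.9) and in range at 13 (3.8 to 5.5). Children are eligible from age 1 with no cap on their number, and Section 5.3.1 notes that "Children with FD have higher incidence of hypophosphatemia compared to adults". About 10 subjects carry the primary estimate, so each is worth 10 percentage points. If the band were really open, it could be settled after the Week 48 values were known, which would weaken the case in Section 4.2 that the endpoint is objective.

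**Working it through.** **1. The plan's own figures.** The exact limits for x of n are the 0.025 quantile of Beta(x, n-x+1) and the 0.975 quantile of Beta(x+1, n-x). With n = 10:

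| x | Lower | Upper | Width | Table 7 width |
|---|---|---|---|---|
| 8 | 0.444 | 0.975 | 0.531 | 0.53 |
| 9 | 0.555 | 0.997 | 0.442 | 0.44 |
| 10 | 0.692 | 1 | 0.308 | not shown |

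Table 7 reproduces. One changed status moves the lower limit from 0.555 down to 0.444 or up to 0.692.

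**2. Table 5 is the Z-score conversion.** Taking the normal range as mean ± 2 SD, Z = -1 lies at lower limit + (upper - lower)/4. In row order this gives 4.925, 4.55, 3.775, 4.175, 3.425 and 3.0. The printed limits are 4.9, 4.6, 3.8, 4.2, 3.4 and 3. Each row is therefore a Z-score scale for people of that age and sex.

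**3. How far adjacent rows disagree.** Share of the old target range that lies above the new ceiling:

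- age 5: (6.8 - 5.9)/(6.8 - 4.9) = 0.9/1.9 = 47%
- age 13, girls: 0.4/1.3 = 31%; boys: 0%
- age 16, girls: 0.5/1.7 = 29%; boys: 1.2/2.0 = 60%
- age 18: 0.5/1.6 = 31%

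**4. How many children a baseline-age reading would affect.** The documents give no age mix, so assume ages spread evenly over 1 to 18. The chance of passing 5, 13, 16 or 18 within 48 weeks is 4 × (48/52.18)/17 = 4 × 0.92/17 = 21.6%. Given a change of row, the two rows disagree on status with average probability 0.26 to 0.44. This range covers uniform phosphate distributions and normal ones with mean Z from -1 to +0.5 (also assumed). Unrounded, the product is 5.7% to 9.6% of children:

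- five children of ten: 0.3 to 0.5 subjects expected; two or more, 3% to 8%
- ten children: 0.6 to 1.0 expected; two or more, 11% to 25%

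One in ten is thus about the top of the expected number, not a ceiling. All these figures compare age at the sample with age at baseline.

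**5. What stays open with age at the sample.** In exact years, the row >18 starts just after the 18th birthday. In completed years, 16-18 runs to the 19th. The two rows together span 3.0 to 5.0 mg/dL and disagree on 3.0-3.4 and 4.5-5.0, which is (0.4 + 0.5)/2.0 = 45% of that span. Only a subject aged 18 when sampled is affected. If all ten were spread evenly over ages 1 to 19 at Week 48, the chance of being 18 is 1/18 = 5.6%. Across the distributions in step 4, these two rows disagree with probability 0.21 to 0.45. That gives 1.2% to 2.5% per subject, or 0.12 to 0.25 subjects in ten, and fewer if some are older.

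**6. Reading the sections together.** Sections 4.3 and 6.1.2 and Table 6 footnote 1 all describe an age- and sex-adjusted quantity. Such a score compares a value with healthy people of the subject's age when the blood is drawn. Table 6 applies it at Week 2 and at eleven four-weekly points from Week 4 to Week 44. The table is therefore in routine use before the Week 48 value exists, and a switch afterwards would be visible against the dosing record.

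**The case for a change.** The best case for a change is that a primary endpoint should not rest on a natural reading when one sentence would settle it. Two cases also survive that reading. At age 18 the Table 5 labels do not say whether years are exact or completed, they do not match the dosing text, and one sentence in Section 6.1.2 blurs the boundary further by combining over 18 with older. For the averaged endpoint in Section 9.1, a child who changes row has no single band.

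Both observations are correct, but they are narrow. The row 16-18 literally includes 18, and a dosing boundary need not coincide with a reference-interval boundary. The labels and the dosing text must still be reconciled by the sponsor, because Table 5 also steers treatment, and no row is preferred here. The averaged endpoint is expressed as a Z-score, so converting each value at its own visit age before averaging is the reading that gives it meaning.

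Listing subjects under both bands, or counting those in range at Week 0, would correct no wrong result. Entry requires "Serum phosphate <10th percentile for age and sex", about Z -1.28 and so already below the target's lower limit of -1, although a value low by chance at screening could be higher at Week 0. Section 9.4.5 already summarizes baseline laboratory values.

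**Conclusion.** No change to the statistical plan follows. The missing sentence is a detail that an analyst would fill the same way: score each value on the Table 5 row for age and sex at that sample. The figure of up to about one subject in ten measures the distance to a baseline-age reading that no section suggests, and it rests on an assumed even age spread and assumed phosphate distributions. The ambiguity that remains concerns a subject aged 18 at the sample with a value of 3.0-3.4 or 4.5-5.0 mg/dL: about 0.12 to 0.25 subjects in ten even if all ten are under 19. That is a labelling slip for the sponsor to reconcile, together with one conversion step left unwritten for a secondary endpoint.

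A changed status would move the estimate by 0.10. Section 9.1 describes preliminary estimation, and no section sets a null value or pass mark for the primary proportion, so 9/10 against 8/10 crosses no decision line. The planned analysis of change from baseline in serum phosphate does not depend on the bands.

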9.4.3 Analysis of the Secondary Endpoint(s)

The 95% Clopper-Pearson exact confidence interval will be provided for the proportions listed in the secondary endpoints. P-values will be calculated. This will be done in the Efficacy Analysis Dataset. If data is missing for categorical outcomes, it will be imputed by either carrying the last observation forward or assuming non-response.

For change from baseline type of secondary endpoints, baseline scores and change over time scores will be summarized by mean, standard deviation, median, and interquartile range. Linear mixed models will be used to analyze the longitudinal change scores collected at multiple post baseline visits if normality assumption is met. The confidence interval will be calculated for change scores at Week 48 based on these models. P-values will be provided as well. All subjects with any data at post baseline visits will be included in these models. For outcomes variables that are collected only at Week 48 post baseline, a 95% confidence interval and the *p* value from the one-sample *t* test will be reported for the change score (from baseline to Week 48)

If the normality assumption is violated when fitting the linear mixed effects models to the raw data, other common transformation methods (such as log or square-root transformation will be explored. If no suitable transformation method is found, *p*-values will be reported by using the exact Wilcoxon signed rank test.

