Following this initial dose titration phase, doses may be titrated at later weeks at the discretion of the PI, if there are concerns about safety, suboptimal efficacy, or if a subject has not yet achieved the target range of serum phosphate. To optimize serum phosphate levels throughout the dose cycle, Investigators may increase the dose of burosumab in 0.5 mg/kg increments in those subjects whose trough serum phosphate level (just prior to the next dose) is below the lower limit of the target range on 2 consecutive measurements performed at 4-week intervals (**Table 6**).

Table 6. Burosumab Dose Titration Scheme

Study Week	Serum Phosphate Level Z-score ¹	Dose Adjustment
Week 2	Less than -1	Increase the dose by 0.2 to 0.5 mg/kg at next dose
Week 2 6, 10 (adults)	> +2 ³	Decrease the dose by 0.2 to 0.5 mg/kg
Week 1, 2, 3 (pediatrics)		
Weeks 4, 8, 12, 16, 20, 24, 28, 32, 36, 40, 44	Less than -1 ²	Increase the dose by 0.2 to 0.5 mg/kg
	-1 to +2	Continue the current dose
	> +2 ³	Skip dose

¹ See **Table 5** for target phosphate levels according to age and sex-adjusted Z-scores

² If phosphate levels are below –1 standard deviation on 2 consecutive measurements, the burosumab dose may be increased by 0.5 mg/kg

³ If phosphate is Z-score > +2, withhold the next dose and reassess the serum phosphate level in 2 weeks. Once serum phosphate is in target range or less than Z-score –1, treatment may be restarted at 0.2 mg/kg less than prior administered dose. If more than 2 sequential phosphate measurements are > +2 Z-score range, the patient may be considered for study discontinuation.

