9.3 Populations for Analyses

- Safety Analysis Dataset: This will include participants who took at least one dose of burosomab.
- Efficacy Analysis Dataset: This will include all participants who received at least one dose of burosomab and have sufficient post-baseline assessment data to enable analyses of study endpoints. For the proportions evaluated at week 48 (the primary endpoint and some secondary endpoints), subjects who have completed 48 weeks of therapy and returned for the week 48 assessment will be included in the analysis.

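### Section 9.4.3 allows two imputation rules for missing secondary proportions without choosing one; this can move the Week 24 result and may understate phosphate above target

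*Combined protocol and SAP*

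**What the plan says.** Section 9.1 lists two secondary proportions. One is "Proportion of subjects achieving serum phosphate levels within the target range (Z-score -1 to +2) at Week 24". The other is "Proportion of subjects achieving mean serum phosphate levels above the target range (Z-score >+2), as averaged across dose cycles between Baseline and Week 48". The second appears only in 9.1, not in the synopsis or the section 3 table, and it is the only proportion that describes phosphate above target.

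For these proportions, section 9.4.3 gives Clopper-Pearson intervals and p-values and names the analysis set: "This will be done in the Efficacy Analysis Dataset". On missing data it says: "If data is missing for categorical outcomes, it will be imputed by either carrying the last observation forward or assuming non-response". It does not say what non-response means for each endpoint.

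Section 9.3 adds a restriction for proportions evaluated at Week 48, which it says are the primary endpoint and some secondary endpoints that it does not name: "subjects who have completed 48 weeks of therapy and returned for the week 48 assessment will be included in the analysis".

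Table 6, footnote 3 (section 6.1.2) links leaving the study to high phosphate: "If more than 2 sequential phosphate measurements are > +2 Z-score range, the patient may be considered for study discontinuation".

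**The concern.** There are two separate problems.

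**Choice of rule.** For a subject who leaves before Week 24 while in range, LOCF records a success with no Week 24 value, and non-response records a failure. The trial is open-label and doses are titrated on serum phosphate throughout, so results are known to the team as they arrive. If the rule is not fixed in the plan, it can be settled after the data have been seen.

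**Direction of the rule.** Non-response is the cautious value for an in-range proportion. For the above-range proportion, the outcome being counted is the unfavourable one. Read literally, non-response then means not above range, which is the favourable value. Under footnote 3 the missingness can be caused by the very event being counted.

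At stake is the credibility of the Week 24 figure, and of the one proportion that describes overshoot in a trial whose section 4.3 deliberately aims for mid-to-high normal phosphate.

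**Working it through.** **Inputs from the plan.** 15 recruited so that 10 have 48 weeks of follow-up, leaving room for up to 5 non-completers (9.2). Two-sided 95% Clopper-Pearson limits (9.2, 9.4.3).

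**Inputs assumed.** The documents give no number of leavers, no reasons for leaving and no Week 24 counts. All counts below are illustrations. A denominator of 15 also assumes that every dosed subject meets the undefined requirement in 9.3 for sufficient post-baseline data.

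**Formula.** For x events in n subjects, lower limit = Beta(0.025; x, n−x+1) and upper limit = Beta(0.975; x+1, n−x), with lower = 0 when x = 0.

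**Check on Table 7.** With n = 10 and true proportions 0.5, 0.6, 0.7, 0.8, 0.9 and 0.95, the widths are 0.626, 0.616, 0.586, 0.531, 0.442 and 0.381. The plan gives 0.63, 0.62, 0.59, 0.53, 0.44 and 0.38. All six agree.

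**Week 24 in range**

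| Assumed case | Non-response | LOCF |
|---|---|---|
| 2 leave before Week 24, both last in range; 11 of the other 13 in range | 11/15 = 73% (0.45 to 0.92) | (11+2)/15 = 13/15 = 87% (0.60 to 0.98) |
| Outer bound: 5 leave before Week 24; 9 of 10 in range | 9/15 = 60% (0.32 to 0.84) | from 9/15 = 60% (none last in range) to 14/15 = 93% (0.68 to 1.00; all last in range) |

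**Above-range proportion.** Assume 15 dosed, k subjects leaving because of values above Z +2, and nobody else above.

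| k | Non-response read as not above | Completers only (9.3) | Leavers counted as above |
|---|---|---|---|
| 1 | 0/15 (upper limit 0.22) | 0/14 (upper limit 0.23) | 1/15 = 7% (0.00 to 0.32) |
| 2 | 0/15 (0.22) | 0/13 (0.25) | 2/15 = 13% (0.02 to 0.40) |
| 3 | 0/15 (0.22) | 0/12 (0.26) | 3/15 = 20% (0.04 to 0.48) |
| 5 | 0/15 (0.22) | 0/10 (0.31) | 5/15 = 33% (0.12 to 0.62) |

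The first two readings both give 0% whatever k is. The last column is the opposite extreme, not the true value: a subject with several high readings need not have a mean above Z +2.

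**9.3 against 9.4.3.** The completer restriction covers some secondary proportions at Week 48. The other secondary proportion is at Week 24, so of the two listed in 9.1 only the above-range proportion can be meant. On that reading 9.3 excludes the leaver, while 9.4.3 imputes the same leaver. The two sections do not say which prevails.

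**The case against.** A reader might infer that the plan definitely scores a subject removed for high phosphate as having no excess, so that the above-range proportion is biased toward zero. The documents do not support that as a statement of fact:

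- Non-response is not defined for this endpoint. LOCF is equally permitted and could carry a high value forward. It could also carry an in-range one, since footnote 3 provides for a repeat measurement after a withheld dose. How LOCF would apply to a mean over cycles is not stated.
- The outcome may not be missing at all. It is a mean over dose cycles, and footnote 3 requires more than 2 sequential high values, so at least three are already on record. No minimum number of cycles is set.
- 9.3 may exclude the subject instead of imputing a value.
- Footnote 3 says only that discontinuation may be considered, and 7.1 separates stopping drug from leaving the study.
- The excess would not be hidden. Section 8.3.3 records laboratory abnormalities needing dose interruption as adverse events, and 9.4.4 tabulates adverse events, including those leading to premature discontinuation of the intervention, in all dosed subjects. Phosphate is also among the clinical safety laboratory tests.

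The assumed counts may also be high. The cited adult trials report hyperphosphatemia in 6 to 7% of patients, managed by dose reduction, and the pediatric trials report none. The second Week 24 case puts all five non-completers before Week 24, although 9.2 allows for them only by Week 48.

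These points remove the certainty about direction and limit the consequence. They do not supply a rule for Week 24, and they do not remove the risk to the above-range proportion: literal non-response and the completer set both leave the subject out of the numerator.

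**Conclusion.** The concern holds in a limited form. The plan permits two imputation rules and selects neither. On the assumed counts this moves the Week 24 proportion from 73% to 87%, with an outer bound of 60% to 93% if all five spare subjects leave before Week 24. That the choice would be made after results are seen is an inference from the open-label design and phosphate-based titration; no section says when it is made.

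For the above-range proportion, understatement is possible but not established. With 2 of 15 leaving for high phosphate and nobody else above, two readings give 0% (0/15 or 0/13), against at most 2/15 = 13% if both are counted as above. The adverse event and safety laboratory summaries would still show the events.

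The imputation sentence sits under the secondary endpoints and does not affect the primary endpoint, which has its own completer set. The trial aims at preliminary estimates, so this is a gap to close before analysis, not a threat to the main result.

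**What to change.** Three changes of wording, with no new data:

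1. **9.4.3, Week 24 in range.** State that a missing value counts as not in range. Name LOCF as a sensitivity analysis only.
2. **9.4.3, above range.** Remove the non-response option for this endpoint. Calculate each subject's mean from all observed on-treatment dose cycles, for every dosed subject (the Safety Analysis Dataset). Add a named sensitivity analysis that counts subjects discontinued for Z > +2 as above range. This should not be the main rule, because a few high values do not make the mean exceed +2, particularly when entry requires phosphate below the 10th percentile. As the main rule it would change the endpoint.
3. **9.3.** State that the completer restriction does not apply to the above-range proportion, so that 9.3 and 9.4.3 agree.

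The cost is a few sentences. The Week 24 figure may come out slightly lower and the above-range figure slightly higher.

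### The non-normality rule for secondary change scores names transformations that fail when a value falls, falls back to p-values only, and is not extended to outcomes measured only at Week 48

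*Combined protocol and SAP*

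**What the plan says.** All of the relevant text is in Section 9.4.3 of the combined protocol and SAP, which separates two kinds of change-from-baseline endpoint.

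- Repeated measures: "Linear mixed models will be used to analyze the longitudinal change scores collected at multiple post baseline visits if normality assumption is met". A confidence interval for the Week 48 change and p-values come from these models.
- Single follow-up: "For outcomes variables that are collected only at Week 48 post baseline, a 95% confidence interval" and a one-sample t-test p-value are given for the change. No normality condition is attached.

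The rule for non-normality comes last and has two steps. It opens: "If the normality assumption is violated when fitting the linear mixed effects models to the raw data". The first step is that "other common transformation methods (such as log or square-root transformation will be explored". The second is introduced by "If no suitable transformation method is found"; p-values then "will be reported by using the exact Wilcoxon signed rank test".

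Section 9.4.1 says that evidence will be judged on point estimates and confidence intervals together with p-values. It names the mixed model as the way missing longitudinal data are handled, under a missing-at-random assumption. Sections 8.3.4, 8.3.6 and 8.3.7 place the PET/CT scan, skeletal survey and bone biopsy at Weeks 0 and 48 only.

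**The concern.** There are three gaps.

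1. **Scale.** The only outcome the mixed model is given is the change score. Log and square root do not apply to a variable that can be negative. If measured values were meant, the plan does not say so, and no model of measured values is described. Two analysts could follow the same text and report different quantities: a transformed difference or a ratio.
2. **Fallback.** When no transformation works, the plan ends with a test and no estimate or interval. The test uses one change per subject, so a subject without a Week 48 value no longer contributes through earlier visits, as they would in the mixed model.
3. **Scope.** The trigger is worded for mixed models, so the t-test outcomes have no written rule.

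Section 3 presents the turnover markers and lesion activity as safety endpoints for the effect on FD lesions. A fall and a rise are both results the analysis must be able to report with an interval, and the scale should be settled before open-label data on at most 15 subjects are seen.

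**Working it through.** **Inputs.** N = 10 completers out of 15 recruited (Section 9.2). The plan gives no effect size or SD for any change score, so the standardized mean change d is an assumption, shown over a range. The plan's only precision figure is Table 7, for the primary proportion. It reproduces (at 0.9 with N = 10, Clopper-Pearson 0.555 to 0.997, width 0.442), but this point uses only its N.

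**Step 1: where the named transformations exist.** At −0.5, 0 and 0.5 the log is undefined, minus infinity and −0.693; the square root is undefined, 0 and 0.707. One negative change defeats both, and a zero change also defeats the log.

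**Step 2: how often a decrease occurs.** With q the probability that one subject declines, P(at least one decrease in 10) = 1 − (1 − q)^10. For normal changes q = Φ(−d).

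| d | q | P(at least one decrease), n = 10 |
|---|---|---|
| 0 | 0.5000 | 0.999 |
| 0.5 | 0.3085 | 0.975 |
| 1 | 0.1587 | 0.822 |
| 1.5 | 0.0668 | 0.499 |
| 2 | 0.0228 | 0.206 |
| 3 | 0.0013 | 0.013 |

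With 15 subjects the figures are 0.925 at d = 1 and 0.292 at d = 2. Normality serves only to turn d into q; for independent subjects the formula holds for any distribution with the same q.

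**Step 3: logging before differencing.** For positive values, log(post/baseline) = log(post) − log(baseline) is finite in either direction. In one simulated set of 10 subjects with skewed positive values, 7 declined and all 10 log ratios were finite. The exact signed-rank test also ran on the same changes.

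**Step 4: what the fallback can deliver.** The smallest two-sided exact signed-rank p is 2/2^n: 0.002 at n = 10, 0.031 at n = 6, 0.0625 at n = 5. The matching interval can reach 95% coverage only from n = 6; at n = 5 the most is 1 − 0.0625 = 93.75%. This matters because PET/CT excludes anyone who would need sedation (Section 8.3.4), and biopsy is confined to adults with capacity and a suitable site (Section 8.3.7).

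**Step 5: the t test with no alternative.** Two-sided type I error at nominal 0.05 and n = 10, simulated with 200,000 samples of mean-zero shifted lognormal changes, is 0.079 for log-scale SD 0.5 and 0.160 for SD 1. These shapes are assumed; the documents give no distribution for PET total lesion activity.

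**The case against.** The strongest reply is that the plan already has an answer. A transformation that cannot be computed is not suitable, so the rule moves to the signed-rank test, which handles decreases. Log and square root are only examples, and raw data may mean measured values, where they are ordinary choices for positive markers. The Wilcoxon sentence closes the section after both branches and suits a single baseline-to-Week-48 change. Medians and interquartile ranges are promised for all change endpoints. The trial is preliminary, and its primary analysis is untouched.

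Most of this stands, and it rules out three stronger readings that a reader might infer.

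- *Subjects who decline would be dropped.* Nothing says so; Section 9.4.3 includes in the models everyone with any post-baseline data.
- *The mean change would be biased upward, by 0.8 SD under a true mean change of zero.* That figure is the mean of a standard normal variable given that it is positive. It requires every decrease to be deleted, and it describes untransformed positive changes, not any log or square-root analysis.
- *Week-48-only outcomes have no remedy at all.* The closing sentence can be read to cover them. What is missing is an explicit statement.

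The reply does not close the gaps in scale, interval and scope. Permitting measured values is not the same as specifying them, and descriptive medians do not replace an interval for the change.

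**Conclusion.** The point holds as a gap in specification with a practical cost. If the rule is applied to change scores, the named transformations will usually be unavailable unless the mean change is large: 82% of the time at 1 SD, about 50% at 1.5 SD and 21% at 2 SD, with 10 subjects and assumed normal changes. The route then ends in a p-value without an estimate or interval, outside the model meant to handle missing data. If it is applied to measured values, the difficulty disappears for positive measures, but the plan does not say that this is intended.

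For outcomes measured only at Week 48, the t test has no stated alternative. Under the assumed skewed shapes its error rate is about 0.08 to 0.16 instead of 0.05. PET/CT, skeletal survey and biopsy are the assessments described as Weeks 0 and 48; I could not confirm the full list because the Schedule of Activities columns before Week 26 were not available to me.

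The effect is confined to secondary endpoints. It should be corrected in the plan, but it does not threaten the primary result.

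**What to change.** Amend Section 9.4.3 as follows.

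1. Define raw data. For strictly positive measures (P1NP, CTX, osteocalcin, bone-specific alkaline phosphatase, 1,25(OH)2D, TmP/GFR), state that any log transformation is applied to measured values before differencing. Analyse log(post/baseline) in the mixed model and back-transform to percent change with a 95% CI. Keep the descriptive summary of absolute change. Log baseline as a covariate is optional with this few subjects.
2. For PET total lesion activity, use the same log ratio when changes are non-normal. Note that this adds a relative-change estimate, since only absolute change is listed for PET.
3. State that the exact signed-rank fallback also covers outcomes measured only at Week 48.
4. Wherever the fallback is used, report the Hodges-Lehmann estimate with its exact interval, and give the achieved coverage if fewer than 6 subjects contribute.

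The cost is SAP wording, with no change to data, visits or sample size. The price is that the estimate becomes a geometric mean ratio. That fits the percent-change endpoints already listed for the mineral and turnover markers, but for PET it is an added quantity that must be labelled as such.
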